Unanticipated problems and adverse events will be reported according to the IRB written guidelines for interventional studies. Serious adverse events will be reported to the Hebrew SeniorLife's IRB, as well as the identified Safety Monitor, within 24hrs by fax or email. A related written report will be submitted within 5 business days of learning of the event, and a submission of the incident via the eIRB system will be completed within one week of learning of the event. This form will record any adverse symptoms and/or study protocol deviations.

All other adverse events/study incidents will be reported to the IRB and Safety Monitor, according to policy, within 5 business days of learning of the event. A related submission of the incident will be completed via the eIRB system within one week of learning of the event. Safety monitoring procedures will be implemented and reviewed by a Safety Monitor (to be determined upon Notice of Grant Award), in accordance with NIA safety policies for human intervention studies.

Prior to the start of the study the Safety Monitor will review the IRB approved protocol, procedure manual and informed consent documents, with regard to participant safety, recruitment, randomization, intervention, data management, quality control, and confidentiality. The Safety Monitor will recommend any necessary changes of the protocol to the PIs and will review and approve revisions. The Safety Monitor will identify relevant data parameters and the format of the information to be regularly reported.

The Safety Monitor will then meet biannually with the investigators to review standardized reports. He/She will review the progress of recruitment and retention of participants, compliance with the protocol, and operating procedures. If they raise concerns about safety issues, they may request additional data and propose specific analyses. They will make recommendations to the PIs regarding recruitment, retention, compliance, and safety issues, and will send a written report to the Program Administrator following each meeting. The Safety Monitor will be sent reports of research activity and summaries of safety monitoring information before each meeting.

Participant discontinuation

The criteria for discontinuing a participant's participation include the participant's request, as well as any unexpected life-threatening or potentially disabling event, including syncope, an injurious non-accidental fall, hemodynamic collapse, stroke, transient ischemic attack, dysrhythmia, renal insufficiency, angina, myocardial infarction, anaphylaxis, acute hemorrhage, or hospitalization for acute illness. These adverse events will be recorded in accordance with IRB requirements and included in the study database. If a determination about continued participation cannot be made according to these criteria, the adverse event report will be faxed to the un-blinded Safety Monitor, who will make the final decision.

Publication Plan

We will register this clinical trial at ClinicalTrials.gov. We also will ensure that informed consent documents for this clinical trial will include a specific statement relating to posting of clinical trial information at ClinicalTrials.gov. Hebrew SeniorLife's Institute for Aging Research has an internal policy in place to ensure that clinical trials registration and results reporting occur in compliance with policy requirements. Results will be disseminated through publications in peer-reviewed medical journals, presentations at national meetings, and announcements on the HSL website and other public media.

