Participants will complete 10 twenty minute brain stimulation sessions (Monday-Friday) over the next two weeks.

tDCS intervention: Similar to our preliminary study, this intervention will consist of 10, 20-minute sessions delivered on Monday-Friday over two weeks. Stimulation will be delivered using the Startim-8™ device and software (Neuroelectrics Corp, Cambridge MA), which enables custom amounts of current to be delivered through an array of up to eight Pi™ gel Ag/AgCl electrodes placed on the scalp according to 10-20 EEG convention. This system also enables the blinding of study staff and participants to stimulation type. At the end of the first session and every other session thereafter, participants will complete a side effects questionnaire.⁵¹ A blinding efficacy questionnaire will also be completed after the final session, on which participants state whether they believe they received tDCS or sham and their confidence in this belief.

Real tDCS: Similar to our preliminary studies, tDCS will be delivered via six gel electrodes with placement and current parameters optimized based on a standard brain to maximize the average normal component of the generated electric field over the left dlPFC. Current delivered by anyone electrode will never exceed 2.0 mA; the total amount of current from all electrodes will not exceed 4 mA. Each 20-minute session will begin and end with a 60-second ramp up/down of current amplitude to maximize comfort.

Sham stimulation: An 'active' sham will be used in which very low-level currents are transferred between the same electrodes used in the active condition throughout the 20-minute session. However, currents will be designed to mimic the cutaneous sensations induced by tDCS yet not significantly influence cortical tissue. This approach effectively blinds participants and operators to stimulation condition and does not affect functional outcomes.⁵²

Visit 14: Follow-Up Assessment (1.5 hours); Participant's Housing site

Follow-up assessment, as described above in Visit 2, will be completed immediately after and 2 weeks after the tDCS intervention.

Visit 15, 16 and 17: Follow-up Personalized Counseling visits (30 minutes); Participant's Housing site

Three bi-weekly in-person counseling sessions will be completed after the tDCS intervention.

Visit 18: Final Assessment visit (1.5 hours); Participant's Housing site

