Final follow-up assessments, as described above in Visit 2, will be completed after 6 weeks of the tDCS intervention.

At the end of visit 18, we will provide the opportunity for participants to continue tracking their FitBit information for up to additional 3 months. If the participant agrees, we will keep the tracking option available for the study team to track the retention of the intervention. The study team will terminate this tracking service by the end of the retention phase.

Materials for recruitment and study conduct

StimFit_Recruitment_Flier_20200108_clean.pptx

StimFit_Recruitment_Flier_notabs_20200108_clean.pptx

StimFit_Recruitment_letter_20200205_tracked IRB edits_clean.doc

Assessment of Protocol Understanding Form.docx

International Physical activity Questionnaire IPAQ short procedure Q by Q and questions.docx

MOCA.pdf

Stim-Fit_Phone_Screen_2020205_clean.docx

Stim-Fit_tDCS_Eligibility_Questionnaire.docx

The PAR Q.docx

gradCPT Instructions_FrailAdults.docx

N-Back_Instruction.docx

TRAILS_V1.pdf

TRAILS_V2.pdf

Trails_v3_corrected.docx
Digit Span.pdf
Blood Pressure Form_42219.docx
DT Balance Assessment 42219.docx
DT familiarization and sitting assessment 42219.docx
DT gait assessment 42219_AlipgEdit.docx
GDS15.pdf
Height and Weight Form 42219.docx
Medical History Questionnaire_1 71318.docx
Medication Review Form_1 42219.docx
Sociodemographic Form 42219.docx
TUG form 42219.doc
BARSE.pdf
ESES worksheet_exercise_self-efficacy_scale_eses_0.docx
SEW_DUR.pdf
SRQ-Exercise_short.pdf
WHAS Pain Questions.docx
tDCS Blinding Efficacy.docx
tDCS Side Effects Questionnaire.docx
Cognitive Reserve Questionnaire.pdf

Data Analysis and Data Monitoring

Data Analysis

This study will enroll 32 participants. We have conservatively planned for approximately 20% attrition and have thus based our statistical plan on complete datasets of $n = 26$.

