Assessment of feasibility endpoints will be based on sample computations, including the screened to enrolled ratio, retention rate, assurance of blinding, and safety assessment (see above). Adverse events (AE) will be organized according to the MedDRA classification system and reported in each DSMB communication both by MedDRA System Organ Class (SOC) and overall. Both the number of individuals with one or more of AEs within each SOC, as well as the total count of all AEs within each SOC, will be reported. These will be accompanied by point and 95% confidence interval estimates of the proportion of individuals who would experience AEs and the total count of AEs per person-time within each SOC, respectively. The latter computation will acknowledge clustering at the level of the participant by using generalized estimating equations (GEE) in estimation with robust variance estimates used for computing confidence intervals.

We will use variance decomposition to generate estimates of within and between-individual variation in functional outcomes that would potentially be used in a subsequent trial (see above), along with confidence interval estimates for said variance measures, in order to assist in planning of the subsequent study. We will also conduct an exploratory analysis of the mean change in these endpoints using mixed-effects linear regression of all time points, with a random effect included at the participant level in acknowledgement of serial correlation of repeated measures. Dependent variables will be the change in outcomes related to average daily activity from baseline to the six-week post-tDCS follow-up period, as well as the change in laboratory-based functional outcomes from baseline to each planned follow-up visit.

Feasibility outcomes:

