- Only the PI and study personnel approved by the IRB and authorized to view PHI will have access to the information
- PHI will not be used during discussion, presentation or publication of any research data.
- Files containing PHI data collected for recruitment and screening purposes will be kept in locked, secured file cabinets accessible only to designated study personnel (research assistants and investigators).

Risks/ Benefit Assessment

Risks

Possible risks associated with physical activity:

Participants will be provided with a personalized goal to increase their average daily physical activity (i.e., step counts) during the study period. Participants are thus expected to increase their physical activity during this period. This activity is expected to be of low to moderate intensity. Potential risks are minimal and most likely transient, including strains, sprains, muscle soreness, light-headedness and physical fatigue. In rare instances, more serious side effects such as an injurious fall may occur.

Tests of walking and physical function:

The proposed walking tests have been adapted from the large-scale, population-based MOBILIZE Boston study (PI: [name]) and multiple completed and ongoing clinical studies within the Clinical Research Laboratory at IFAR. They have been designed to be safe for individuals of varying risk and conditioning levels including older adult fallers. The physical activity associated with these tests is of low to moderate intensity. Potential risks include strains, sprains, muscle soreness, and light-headedness. In rare instances, more serious side effects such as an injurious fall may occur. For all functional tests, a trained "spotter" will stand behind or close to the subject to provide stabilizing assistance if necessary. Subjects will be instructed to stop performing or skip any test that makes them feel uncomfortable. Adequate rest will be given in between each test, and any reusable equipment will be cleaned with disinfectant after each use.

Transcranial direct current stimulation (tDCS):

tDCS has been widely used during the last decade demonstrating non-significant risk to participants. Expected side effects include:

- 1) Sensations reported by subjects under the electrodes: (These sensations can sometimes continue throughout and for a brief period following completion of the tDCS but usually resolve shortly after the initiation of tDCS)
Mild tingling (20-70%)
Light itching (30-40%)

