Slight burning (10-22%) Discomfort or mild pain (10-18%)

- 2) Other effects that can occur both during and after tDCS include:
Mild fatigue (15%)

Skin redness (20%)
Headache (10-15%)
Difficulties in concentration (11%)

3) Additionally, the following rare side effects have been described:

Nausea (<1%)
Nervousness (<1%)

Although it has never been reported in tDCS, seizures are a theoretical risk. Individuals with a history of seizures and/or a diagnosis of epilepsy will therefore be excluded from this study.

Tests of mental function:

Risks associated with answering the cognitive test questions are minimal, but participants may experience mental fatigue and/or anxiety during this form of testing.

Minimizing Inconvenience

We will minimize the risk to subjects in this study by excluding those with conditions listed in the exclusion criteria. The proposed protocol requires multiple visits and therefore considerable participant burden with respect to time and effort. Our study team has a strong track record of successful clinical research requiring similar participation, and retention has been high in these projects. The Clinical Research Laboratory at IFAR is located next to a cafeteria and equipped with comfortable seating, a TV, movies, books and magazines to keep individuals occupied during resting periods. Several additional strategies will be employed to minimize participant burden and maximize adherence to the protocol. We will: Develop a personal relationship between participants and members of the staff by matching research assistants with individual participants. Schedule appointments at convenient times with familiar staff. Explain to participants all aspects of their participation and follow up. We will demonstrate and practice study procedures before beginning data collection. Provide reminders of all appointments and follow-up phone calls. Include personal notes in the participant's data file to remember events in the life of the participant; these can be commented on at the next visit (e.g., birthday, birth of a grandchild). Provide snacks during all visits. Provide transportation for all visits, if required. Provide valet or dedicated, on-site parking spaces. Compensate participants for visits.

COVID-19:

During the COVID 19 quarantine and social distancing procedures, precautions will be taken to minimize contact when possible by performing teleconferencing and frequent check ins with participants on a remote basis.

Potential Benefits

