Describe the type remuneration and the timing of remuneration to study procedures e.g. participants will be provided with \$50 per study visit, to be distributed as visits are completed, etc.

Participants receive up to \$160 for taking part in this study. Participants will also receive a FitBit and will be able to keep it when the study has ended if they wish. Specifically, participants will receive the following amounts for each visit completed:

Visit 1 - In-person screening visit - \$10 Visit 2 – Baseline visit - \$10

Visits 3- 12: Brain stimulation – 10 visits over two weeks; \$10 for each visit= total of \$100

Visits 13-14: Follow-up assessment visits - \$10 for each visit = \$30 total for completion of all 3 follow-up visits.

Visit 15: Final in-person counseling session - \$10 Visit 16: Final follow-up study assessment - \$10

Participants will receive a check in the mail within eight weeks of study participation.

Participant Withdrawal

Participation may be terminated at the discretion of the PI, if the PI feels that study discontinuation is necessary to protect the participant, or that there are unmanageable factors which will interfere significantly with the study procedures and/or interpretation of results. The study participant will be informed of this and withdrawn from the study. The participant can, at any time, request the study be terminated and to be withdrawn. Any previously collected data prior to termination/withdrawal will be maintained in the study data set.

Adverse Event Reporting

An adverse event is any untoward medical occurrence in a participant, whether or not it is causally related to the study. An adverse event can therefore be any unfavorable and unintended sign (including an abnormal laboratory finding, for example), symptom or disease temporally associated with the study. Adverse events will be recorded on the appropriate case report forms and source documents. The investigator and/or trained staff member will evaluate all adverse events as to their severity and relation to the test article. The severity of adverse events will be graded as follows:

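### The tDCS side effects questionnaire is scheduled at alternate sessions only, so the planned adverse event summaries are likely understated for mild stimulation effects

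*Protocol*

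**What the plan says.** The Protocol's tDCS intervention paragraph sets the course: "this intervention will consist of 10, 20-minute sessions delivered on Monday-Friday over two weeks". It then sets the side-effect collection: "At the end of the first session and every other session thereafter, participants will complete a side effects questionnaire". At the last session it names a different form: "A blinding efficacy questionnaire will also be completed after the final session".

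The Risks section opens its second list with "Other effects that can occur both during and after tDCS include" and names mild fatigue, skin redness, headache and difficulty concentrating.

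The Data Analysis section counts safety among the feasibility endpoints. By MedDRA system organ class it plans "point and 95% confidence interval estimates of the proportion of individuals who would experience AEs", and also a count of events per person-time.

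The form appears in the materials list only as "tDCS Side Effects Questionnaire.docx". Its recall period is not given, and the citation attached to it (51) lies beyond the end of the reference list, which stops at 48.

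Separately, Adverse Event Reporting begins: "An adverse event is any untoward medical occurrence in a participant, whether or not it is causally related to the study". It requires events to be entered on case report forms, but does not say when or how participants are asked. The SAP says nothing on side effects; its feasibility outcomes are session completion rates.

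**The concern.** The form is used at half the sessions, and at the end of the visit, while the Protocol itself expects some effects to appear later. The remaining scheduled contacts do not close the gap. Visits 14 and 18 repeat the Visit 2 battery, which has no side-effect item. The telephone calls are meant for checking in, reviewing activity and answering questions.

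At stake is the safety part of a pilot's feasibility evidence. Mild effects such as a headache that evening or redness the next morning are what participants often do not mention unless asked. The two planned summaries can be lowered by skipped sessions but not raised by them, and their confidence intervals would not reflect the loss.

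**Working it through.** The documents give no tolerability rate or precision that depends on this schedule, so there is no figure to reproduce.

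**Inputs from the Protocol:** 10 sessions; form at the first and every other session; 16 participants per arm (Participant Selection); headache 10-15% (Risks; whether per session or per participant is not stated). **Assumptions, not in the documents:** per-session rates, within-person correlation and time trends below.

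**1. Coverage.** Sessions 1, 3, 5, 7 and 9 are covered: 5/10 = 50%. Session 10 is not. (*Every other* could also be read as all the rest; the wording would then need changing anyway.)

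**2. Effect in k random sessions, form covering only its own session, nothing volunteered.** P(miss) = C(5,k)/C(10,k).
- k = 1: 5/10 = 50%
- k = 2: 10/45 = 22%
- k = 3: 10/120 = 8%

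**3. Headache as an upper-end illustration.** Assume the rate is per participant per course, each headache affects one session, and none is volunteered. Expected cases among 16 are 16 × 0.10 = 1.6 to 16 × 0.15 = 2.4; recorded cases are half, 0.8 to 1.2. The chance that the tDCS arm shows none:
- at 10%: 0.90^16 = 19% becomes 0.95^16 = 44%
- at 15%: 0.85^16 = 7% becomes 0.925^16 = 29%

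**4. Proportion with at least one report, effects able to recur.** For independent sessions, 1 − (1 − p)^n. For within-person correlation r, a beta-binomial with a = p(1 − r)/r and b = (1 − p)(1 − r)/r, where P(no report) is the product of (b + i)/(a + b + i) for i = 0 to n − 1.

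| Rate per session | r | 5 sessions | 10 sessions | Shortfall (points) |
|---|---|---|---|---|
| 1% | 0 | 4.9% | 9.6% | 4.7 |
| 10% | 0 | 41.0% | 65.1% | 24.1 |
| 10% | 0.3 | 27.1% | 35.9% | 8.8 |
| 10% | 0.6 | 18.5% | 22.1% | 3.6 |
| 10% | 1 | 10% | 10% | 0 |
| 40% | 0 | 92.2% | 99.4% | 7.2 |

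**5. Count per person-time.** With a flat rate, a current-session form and no other capture, 5 sessions of events over 10 sessions of time gives about half the true count.

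**6. Mean per-session rate (not a planned summary).** Flat 20%: 20% either way. Session 1 at 40%, the rest 20%: sampled (0.40 + 4 × 0.20)/5 = 24%, full (0.40 + 9 × 0.20)/10 = 22%. Steady rise from 13% to 40%: 25% sampled, 26.5% full. So this measure can go either way.

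**7. Recall period.** If the form asks about the time since the last form, sessions 2, 4, 6 and 8 and most after-effects are reached by recall. The time after session 9, and session 10 itself, still are not. With a Monday start, recall at session 7 (Tuesday) reaches back across a weekend to session 5 (Friday).

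**The case against.** The strongest reply is that a second route exists. The adverse event definition is broad enough to include a headache after session 4 or session 10. Such events must be recorded, graded and related to the test article, and non-serious ones reported within 5 business days. Staff see participants on every stimulation day, and participants can contact the team at any time. Nothing says the Data Analysis summaries come from the questionnaire alone. This stands, so a reader who infers that effects at half the sessions go unrecorded goes too far. What is missing is scheduled asking.

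A reader might also infer that every after-session effect is lost. The documents do not support that, because the recall period is unknown (step 7). Nor do they support saying that side-effect rates in general come out too low: step 6 shows a per-session rate can be unbiased or too high. The statement is confined to the two summaries that are planned.

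It is tempting to add that the next trial would be planned on these rates. The planning inputs the Protocol names are variance components, the screening ratio and the probability of completion.

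Finally, alternate-session sampling may be a deliberate economy: stimulation visits last 30 minutes, 20 of them stimulation, and the Protocol acknowledges considerable burden. That is fair, but it does not explain leaving out the last session, where another form is already completed.

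**Conclusion.** The point holds as a gap in structured safety capture. On the natural reading, the form is used at 5 of 10 sessions and not at the last, and no provision schedules asking about effects at the other sessions or after session 10. Unless the recall period covers them, those effects depend on spontaneous report.

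The planned proportion of participants with an event and the planned count per person-time are therefore likely understated for mild effects. The size is uncertain. For the proportion it is zero if effects recur fully within a person, and about 24 points at an assumed 10% per session with independent sessions. A single-session effect that is never volunteered is missed 50% of the time. The headache figures belong at that upper end.

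Both arms share the schedule, so it creates no false difference between them. The absolute size of a real difference could change. The primary functional outcome, sample size, power and type I error are unaffected. Confidence is high on the gap and moderate on the size of the bias.

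**What to change.** Reword the sentence so that the existing side effects questionnaire is completed at the end of all 10 sessions. From session 2, add one item on effects since the previous session ended. Ask that item once more at the post-stimulation assessment (Visit 14) to cover the time after session 10; the SAP places the post-stimulation measurement within three days of the last session. State the form's recall period. Report during-session and after-session effects separately, each with its denominator (sessions queried, or participants with at least one completed form).

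The cost is a wording change, five more completions of an existing form per participant, one added item, a few extra minutes per visit and slight participant burden. No new visit is needed.

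If collection is already complete, state which sessions were queried and over what recall period, and label the rates accordingly.

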The Safety Monitor will then meet biannually with the investigators to review standardized reports. He/She will review the progress of recruitment and retention of participants, compliance with the protocol, and operating procedures. If they raise concerns about safety issues, they may request additional data and propose specific analyses. They will make recommendations to the PIs regarding recruitment, retention, compliance, and safety issues, and will

The investigator and/or trained staff member will evaluate all adverse events as to their severity and relation to the test article. The severity of adverse events will be graded as follows:

- Mild: Awareness of a sign or symptom but easily tolerated.
- Moderate: Discomfort sufficient to cause interference with usual activity or to affect clinical status.
- Severe: Incapacitating with inability to do usual activity or to significantly affect clinical status.
- Life Threatening: The participant was at immediate risk of death from the adverse event as it occurred.

The Investigator will also assess the relationship of any adverse event to study, based upon available information, using the following guidelines:

- 0 = Unlikely: No temporal association, or the cause of the event has been identified.
- 1 = Possible: Temporal association, but other etiologies are likely to be the cause; however, involvement of the study procedures cannot be excluded.
- 2 = Probable: Temporal association, other etiologies are possible, but not likely.

A serious adverse event is any experience that results in any of the following outcomes: death, is life threatening, inpatient hospitalization or prolongation of hospitalization, a persistent or significant disability/incapacity. Important medical events that may not result in death, be life-threatening, or require hospitalization may be considered a serious adverse event when, based upon appropriate medical judgment, they may jeopardize the patient or participant and may require medical or surgical intervention to prevent one of the outcomes listed in this definition.

Unanticipated and adverse event reporting

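### Adverse events are to be estimated only by organ class and overall; severity, the side effects questionnaire and arm are not used, so no expected tDCS effect gets a planned rate

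*Protocol*

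**What the plan says.** Data Analysis (protocol, Data Analysis and Data Monitoring) names safety among the feasibility endpoints. AEs are to be "reported in each DSMB communication both by MedDRA System Organ Class (SOC) and overall". The two summaries are "Both the number of individuals with one or more of AEs within each SOC, as well as the total count of all AEs within each" organ class. On estimation the section adds: "These will be accompanied by point and 95% confidence interval estimates of the proportion of individuals who would experience AEs"; the second summary is turned into a count per person-time, with GEE and robust variances for the intervals. No summary by term, symptom, severity, relatedness or arm is described. The SAP contains no safety analysis; its feasibility outcomes are the completion rates for the two kinds of session.

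Other sections collect more detail than this analysis uses:

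- **Adverse Event Reporting** defines AEs broadly: "An adverse event is any untoward medical occurrence in a participant, whether or not it is causally related to the study". It says "The severity of adverse events will be graded as follows".
- **Safety Monitoring** gives the four grades, from mild to life threatening. The third reads "Severe: Incapacitating with inability to do usual activity or to significantly affect clinical status".
- **Experimental Procedures (tDCS intervention)** adds symptom-level data: "At the end of the first session and every other session thereafter, participants will complete a side effects questionnaire".
- **Risks (tDCS)** lists expected effects one by one, most with a percentage; headache, for example, is put at 10-15%.

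**The concern.** The protocol states its expected harms symptom by symptom, collects a side effects questionnaire and grades every AE, but the planned estimates stop at organ class. A rate for an organ class cannot be set beside a rate for headache or burning. A count that ignores grade cannot show whether the events were mild. Yet the protocol's risk-benefit argument (Potential Benefits) relies on the risks being slight, short-lived and uncommon, and the pilot is meant to inform a later trial.

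The gap exists whichever way the questionnaire is handled. If its symptoms are entered as AEs, which the broad definition would allow, expected skin sensations fill much of the overall figure. If they are not, the questionnaire has no analysis. In both cases none of the listed tDCS effects gets a planned rate.

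**Working it through.** The AE plan states no precision or sample-size figure, so there is nothing of the plan's own to reproduce. The check asks how the planned overall figure would behave if questionnaire symptoms were counted as AEs.

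**Inputs** (protocol, Risks, tDCS; nausea and nervousness, each below 1%, are left out):

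| Effect | Low end | High end |
|---|---|---|
| Tingling | 0.20 | 0.70 |
| Itching | 0.30 | 0.40 |
| Burning | 0.10 | 0.22 |
| Discomfort or pain | 0.10 | 0.18 |
| Fatigue | 0.15 | 0.15 |
| Skin redness | 0.20 | 0.20 |
| Headache | 0.10 | 0.15 |
| Concentration difficulty | 0.11 | 0.11 |
| **Sum** | **1.26** | **2.11** |

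The group size of 16 per arm comes from Participant Selection. Assumptions: the rates apply per stimulated participant, and each symptom counts once per person.

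**Composition of expected reports.** Local sensations plus redness (tingling, itching, burning, discomfort or pain, redness):

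- Low: 0.90/1.26 = 71%. High: 1.70/2.11 = 81%.
- Tingling plus itching alone: 0.50/1.26 = 40%; 1.10/2.11 = 52%.
- Headache: 0.10/1.26 = 7.9%; 0.15/2.11 = 7.1%.

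**Share with at least one effect, assuming independence**, 1 − ∏(1 − pᵢ):

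- Low: 1 − 0.8×0.7×0.9×0.9×0.85×0.8×0.9×0.89 = 75.3%. With headache doubled from 10% to 20%, the factor 0.9 for headache becomes 0.8 and the result is 78.0%.
- High: 1 − 0.3×0.6×0.78×0.82×0.85×0.8×0.85×0.89 = 94.1%. With headache doubled from 15% to 30%, it is 95.1%.

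In a group of 16, these shifts are 0.0275×16 ≈ 0.4 and 0.0105×16 ≈ 0.2 of a participant. Headache itself would go from 1.6 to 3.2 expected participants, or from 2.4 to 4.8.

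**Sensitivity to independence.** With full overlap the share equals the largest single rate, 30% or 70%, and doubling headache does not move it at all (20% is below 30%; 30% is below 70%). The shift would approach the full 10 or 15 points only if the extra headaches fell mainly on people with no other symptom.

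**What a symptom-level row would give.** At a true rate of 10-15%, the chance that at least one of 16 reports headache is 1 − 0.90¹⁶ = 0.81 to 1 − 0.85¹⁶ = 0.93. Clopper-Pearson 95% intervals are 1.6-38.3% for 2/16 and 7.3-52.4% for 4/16. The documents give no severity distribution, so the expected share graded moderate or worse cannot be computed.

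**The case against.** Several objections have force.

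- **Whether sensations are counted.** No passage says questionnaire symptoms become AEs; they are described as expected effects and have their own form. A reader might infer that tingling and itching swamp the figures. The documents do not support that: it depends on an unstated coding rule, and those two symptoms are only 40-52% of expected reports even if it applies. It is local sensations and redness together that dominate, and only in the overall figure and in whichever classes receive them. The documents do not assign symptoms to classes.
- **Individual review.** A reader might also infer that a serious event would be lost among trivial ones. It would not. Every AE is graded and assessed for relatedness; serious events go to the IRB and Safety Monitor within 24 hours and others within 5 business days. The weakness is in the aggregate estimates only.
- **The Safety Monitor's powers.** The monitor identifies the data and format to be reported and may ask for further analyses, so a finer table can be produced under the existing plan. This softens the gap, but such a table is still not pre-specified for the final report.
- **The questionnaire's content.** Its items are not reproduced, and nothing shows that they carry the AE severity grades. A table must not assume that they do.
- **Precision.** At 16 per arm, 2/16 and 4/16 have heavily overlapping intervals, so the finer table would not establish a doubling of headache either. Its value is an interpretable point estimate beside a stated expectation, not a test.

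**Conclusion.** The omission stands on the text: one safety analysis, at organ-class and overall level, with severity, questionnaire and arm unused. It follows that none of the listed tDCS effects gets a planned rate and that the output cannot show whether harms were mild.

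The dilution figures (71-81% of reports; 75.3% to 78.0%, or 94.1% to 95.1%) are conditional. They hold only if questionnaire symptoms are entered as AEs, with the protocol's rates applying per stimulated participant and each symptom counted once; the proportions also assume independence.

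Arm matters because the sham is designed to reproduce the skin sensations of real stimulation, so pooled proportions could not fairly be compared with published-type tDCS rates. In a 32-person pilot with descriptive safety reporting, this is a worthwhile, inexpensive improvement. It alters no efficacy estimate or decision rule and raises no question of clinical management.

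**What to change.** Amend the protocol's Data Analysis section and add a safety paragraph to the SAP:

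1. Keep the organ-class listing, and state whether questionnaire symptoms count as AEs.
2. Add one table by randomised arm. For each AE term and each questionnaire symptom, give the number and proportion of participants who ever reported it, with an exact 95% interval.
3. For events recorded as AEs, show the worst grade on the protocol's four-level scale. For questionnaire items, show whatever intensity the form records.
4. Add one line per arm for participants with any AE graded moderate or worse.
5. Set only the real-tDCS arm beside the expected rates in the Risks section.

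The cost is a few sentences and one table, with no added visits or assessments described here. The table should be labelled descriptive, because the intervals are wide at 16 per arm.
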